October 19, 2019

Manuscript title: **Acute effects of High Intensity Interval Training (HIIT) and Steady State Moderate Intensity Training (SSMIT) on Intraocular Pressure among Sedentary Individuals.**

I am pleased to submit the manuscript entitled '*Acute effects of High Intensity Interval Training (HIIT) and Steady State Moderate Intensity Training (SSMIT) on Intraocular Pressure among Sedentary Individuals.*'

Intraocular pressure (IOP) remains the main treatable risk factor for glaucoma, which causes blindness in 4.5 million people worldwide, accounting for slightly more than 12% of all global blindness. Thus, treatment of glaucoma has traditionally been aimed at reducing the IOP, medically or surgically. Exercise is one of the factors that has been proven to influence IOP.

Our study investigated the effects of both forms of aerobic exercise on IOP in sedentary individuals. We believe that our findings would contribute valuable information for the use of exercise in the management of intraocular pressure. In addition, our study also provides useful information for future research on the effect of exercise in glaucoma management.

Sincerely,

DR [name]
Email: [contact]

RESEARCH PROTOCOL

Title of research: Acute effects of High Intensity Interval Training (HIIT) and Steady State Moderate Intensity Training (SSMIT) on Intraocular Pressure among Sedentary Individuals.

Overall the study can be divided into 3 phases :

Phase 1 : Recruitment Phase

Phase 2 : Baseline Assesment Phase

Phase 3 : Exercise Protocol Phase

Phase 1 : Recruitment Phase

1. Application to join the study will be open to all staff of University Malaya Medical Center.
2. 40 participants will be chosen based on the inclusion and exclusion criteria through a randomized method.
3. Consent, Patient Information Sheet and Global Physical Activity Questionnaire will be given and taken.

Inclusion criteria:

1. Healthy volunteers or patients able to undergo different intensity of exercise based on their VO₂max
2. Able to sign informed consent
3. Patients having medical problems to be well-controlled

Exclusion criteria

1. Previous ocular trauma
2. Previous surgery in the eligible eye
3. Known case of glaucoma/glaucoma suspect (IOP > 21mmHg)
4. History of glaucoma laser procedure/surgery within prior 6 months in eligible eye
5. Unable to undergo IOP measurements

6. Unable to give informed consent
7. Undiagnosed visual conditions
8. Uncontrolled medical condition such as:

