 - end stage renal failure
 - uncontrolled diabetes
 - uncontrolled hypertension

Phase 2: Baseline Assessment Phase

Participants will do the assessment in the Sports Medicine Performance Lab

Baseline assessment parameters:

- Blood pressure
- Resting HR
- HRmax
- Body Impedance Analysis (BIA)
- Waist Circumference, Hip Circumference, Height
- VO₂max: 6 minute Astrand Rhythmic cycle ergometer test
- Baseline IOP

*For intraocular pressure assessment, all subjects will be measured at 10am (\pm 1hour) to avoid diurnal variation.

*Subjects are required to avoid any liquid/caffeinated drinks 1 hour prior to IOP measurement.

Phase 3 : Exercise Protocol Phase

[figure not shown]
1. The exercise sessions will be conducted in controlled room temperature (20-23C) between 8.00am to 11.00am using a Monarch 939E Bicycle Ergometer.
2. Participants are not allowed to drink water 2 hours prior until 30 minutes after the exercise session.
3. Each participant will perform both sessions (SSMIT & HIIT) based on the group they were assigned to with a 4 day wash out period between protocols.
4. Each protocol will have the participant cycle for 30 minutes at a speed of 60 rpm.
5. The SSMIT protocol: participants cycle at a moderate intensity of 50% of their VO₂R.

6. The HIIT protocol: consists of 10, 3-minute cycles (1 minute high intensity of 75% VO₂R and 2 minutes low intensity 35% VO₂R).
7. Participants HR will be monitored during the protocols using a HR monitor (Polar Heart Rate Monitor T31-Coded).
8. Before each session, the participants IOP of the right eye will be measured using an iCare rebound tonometer TA01i and repeated IOP measurements will be taken immediately after (0min), 5, 10, 15, 20 & 30 minutes after the exercise session.
9. Each IOP measurement will be taken on the participants right eye with them seated and contralateral eye focused on a distant object.
10. The examiner is blinded to which protocol the participant performed.

Schedule for phase 3:

Week 1: Group A (HIIT) & Group B (SSMIT) : 10 participants/day

Week 2: Group A (CME) & Group B (SSMIT) : 10 participants/day

Statistical Analysis

Data analysis will be conducted using Statistical Package for Social Studies (SPSS) software version 23.

Values for continuous variables are presented as means and standard deviation.

Prior to data analysis normality of continuous variable will be tested using skewness and kurtosis.

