A two-way repeated measure ANOVA will be conducted to evaluate the effect of exercise on IOP and interaction between groups and time followed by using Bonferroni post-hoc test for pairwise comparison.

A paired sample T test will be conducted to assess the difference of IOP levels between interventions. A value of $p < 0.05$ is considered as significant.

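### The two-way repeated-measures ANOVA keeps only participants with all 14 pressure readings, so scattered missing values would shrink its sample and separate it from the paired t-test

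*Combined protocol and SAP*

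**What the plan says.** The Statistical Analysis section states: "A two-way repeated measure ANOVA will be conducted", covering the exercise effect on pressure and a group-by-time interaction. Bonferroni pairwise comparisons follow, then a paired t-test between the two interventions. On software it says: "Data analysis will be conducted using Statistical Package for Social Studies (SPSS) software version 23". No SPSS procedure is named.

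The data structure comes from earlier sections. On sample size, the Recruitment Phase says "40 participants will be chosen based on the inclusion and exclusion criteria through a randomized method". Under the Exercise Protocol Phase, item 3, every participant does both sessions, "based on the group they were assigned to with a 4 day wash out period between protocols". Item 8 gives one reading before exercise ("Before each session, the participants IOP of the right eye will be measured using an iCare rebound tonometer TA01i") and six after it ("repeated IOP measurements will be taken immediately after (0min), 5, 10, 15, 20", with a last one at 30 minutes).

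The documents contain no missing-data rule, analysis-set definition, dropout allowance, or provision for repeating a visit or replacing a participant.

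**The concern.** Repeated-measures ANOVA as it is usually run in SPSS needs a full row of data for each person. With protocol and time both within-participant, that row has 14 entries. A person with 13 good readings and one failed reading contributes nothing to the ANOVA.

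Two things follow if readings are missing. The ANOVA, which carries the protocol-by-time question, loses far more data than was actually missed. And the paired t-test, if run time point by time point, needs only two readings per person and so keeps people whom the ANOVA has dropped. The plan's two analyses of the same comparison would then describe different groups, and nothing says which governs.

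**Working it through.** **Inputs from the documents.** 40 participants, 2 sessions each, and 1 + 6 = 7 readings per session. That is 7 × 2 = 14 readings per person and 40 × 14 = 560 in all. The plan gives no power, effect size, standard deviation or dropout figure, so the choice of 40 cannot be reproduced.

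**Assumed input.** Each reading is missing independently with probability q. The documents give no value, so a range is shown.

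**Scattered missing readings.** Expected complete cases in the ANOVA are 40 × (1 − q)^14. A paired t-test at one time point keeps 40 × (1 − q)^2. Observed readings are 560 × (1 − q), and the ANOVA uses 560 × (1 − q)^14 of them.

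| q | (1 − q)^14 | People in ANOVA | People in per-time t-test | Readings missing | Observed readings discarded by ANOVA |
|---|---|---|---|---|---|
| 0.5% | 0.9322 | 37.3 | 39.6 | 2.8 | 557.2 − 522.0 = 35.2 |
| 1% | 0.8687 | 34.7 | 39.2 | 5.6 | 554.4 − 486.5 = 67.9 |
| 2% | 0.7536 | 30.1 | 38.4 | 11.2 | 548.8 − 422.0 = 126.8 |

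In 20,000 simulated trials at 2%, the mean number of complete cases was 30.1, with the central 95% running from 25 to 35. A model on all available readings would use about 549 of 560 values at that rate.

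**Clustered loss.** Independence is the unfavourable case. If the same 11.2 missing readings at 2% came as whole lost sessions, they would amount to 11.2 / 7 = 1.6 sessions, and about 38 people would remain complete.

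**Different factor structure.** If group were instead entered as a between-participant factor on 7 readings, sessions would drop separately and 40 × (1 − q)^7 would be complete per session: 38.6, 37.3 and 34.7 at the three rates.

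**Missed second visit.** Suppose four people miss it, two having done each protocol. The ANOVA keeps 36. For the contrast at one time point, a mixed model with within-person correlation ρ has information proportional to 36/(1 − ρ) + 2, against n/(1 − ρ) for n complete pairs. The effective number is therefore 36 + 2(1 − ρ), which is 37.0 at ρ = 0.5 and 36.4 at ρ = 0.8. Both correlations are assumed.

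**The case against.** The strongest reply is that little may be missing. Participants are staff of one medical centre, people who cannot have their pressure measured are excluded, and a session is 30 minutes of cycling plus 30 minutes of readings. With complete data the ANOVA and a mixed model give nearly the same answer. The deletion is inferred from the method and software, not stated, and the wording about groups and time leaves the factor structure open. For a missed visit, the likelier kind of loss, the mixed model recovers almost nothing and the paired t-test loses the same people. All of this stands, and it limits the size of the point. It does not remove it: nothing in the plan offsets the deletion, and a between-participant reading would ignore the pairing that the crossover provides.

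Three stronger readings are tempting, and the documents do not support them.

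- **A stated loss of power.** An effect with 80% power in a paired t-test at n = 40 (0.454 SD of the paired difference, two-sided 5%) would have 74% at n = 35 and 67% at n = 30. These figures should not be used. They describe neither the ANOVA interaction nor a per-time t-test, which would keep about 39 or 38 people and have about 79% or 78% power. The 80% starting point is also assumed.
- **Selection through poor tolerance of HIIT.** The documents give no reasons for non-return, and this route exists only where HIIT comes first. If non-return depended on unrecorded tolerance, the mixed model's missing-at-random assumption might fail as well.
- **Crowding as a cause of missed readings.** The schedule lists "10 participants/day", but the numbers of ergometers and examiners are not stated.

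**Conclusion.** The point holds as a conditional weakness of the chosen method. If some readings are missed here and there, the ANOVA would discard many more than were lost: about 37, 35 or 30 of 40 participants would remain at 0.5%, 1% or 2% missing per reading, against about 38 to 40 in a per-time paired t-test.

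This rests on four assumptions: the missingness rates, their independence, protocol and time both being within-participant factors, and the t-test being done at single time points. Clustered loss would make the effect smaller. The conclusion concerns avoidable loss of data and mismatched samples; no figure for lost power or bias can be drawn from the documents. It is worth correcting because the better method needs no new data.

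**What to change.** In Statistical Analysis, replace the repeated-measures ANOVA with a linear mixed model on all available readings (the MIXED procedure in SPSS), and specify:

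- fixed effects for protocol, time, protocol-by-time and period;
- a random participant effect;
- a within-session residual correlation that allows for the uneven spacing of the readings. Use an unstructured form first (7 × 8 / 2 = 28 parameters, estimated from up to 80 sessions), with a spatial power structure as the named fallback if it does not converge. Confirm that the installed version offers the fallback;
- HIIT-minus-SSMIT contrasts at each time taken from this model with the Bonferroni adjustment, so that all comparisons use one sample;
- that participants with only one session are kept;
- that the analysis assumes data are missing at random, with the number of participants and readings used reported.

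The Schedule for phase 3 must also be reconciled with item 3. It lists SSMIT for Group B in both weeks and an undefined term, CME, for Group A in week 2, whereas item 3 has everyone doing both protocols. The period effect and the within-person contrast depend on which is meant.

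The cost is a slightly more complex model to report. No visits, measurements or participants are added.

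### With no resting session, the pre-to-post change in IOP cannot by itself be attributed to exercise, although the planned ANOVA is to evaluate the effect of exercise

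*Combined protocol and SAP*

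**What the plan says.** The Statistical Analysis section assigns two tests.

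- The first is a two-way repeated measures ANOVA, whose purpose is to "evaluate the effect of exercise on IOP and interaction between groups and time". Pairs of means are then compared with a Bonferroni correction.
- The second is for the two protocols: "A paired sample T test will be conducted to assess the difference of IOP levels between interventions".

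The threshold is a p value below 0.05; whether tests are one- or two-sided is not stated.

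Under Phase 3 (Exercise Protocol Phase), each participant does both SSMIT and HIIT (item 3), each as 30 minutes of cycling (item 4). IOP is read in the right eye before the session and at 0, 5, 10, 15, 20 and 30 minutes after it (items 8 and 9). Sessions run "between 8.00am to 11.00am" (item 1). Item 2 reads: "Participants are not allowed to drink water 2 hours prior until 30 minutes after the exercise session". The examiner is blinded to the protocol performed (item 10); blinding to time point is not mentioned.

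Under Phase 2 (Baseline Assessment Phase), IOP is to be measured within an hour of 10am "to avoid diurnal variation". No resting session is described anywhere in the text.

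**The concern.** The ANOVA sentence names an effect of exercise and, separately, an interaction between groups and time. Every condition in the design is exercise, so the protocol factor can only contrast one form of cycling with the other. The term left to speak to exercise as such is the change from before to after, and no unexercised course exists to compare it with.

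The protocol itself treats time of day as something that moves IOP. Clock time, hours without water and number of readings all increase along the same axis as the ANOVA time factor. A significant time effect could then be reported as exercise changing IOP even if the same change would have occurred at rest. This matters because the cover letter presents the findings as informing the use of exercise to manage IOP. That is a claim about exercise itself, not about HIIT relative to SSMIT.

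**Working it through.** The documents give no effect size, SD, power or sample-size calculation, so there is no planned figure to reproduce.

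**1. Which term addresses exercise**

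- Protocol main effect: HIIT against SSMIT, averaged over readings.
- Protocol-by-time interaction: whether the IOP course differs between HIIT and SSMIT.
- Paired t test: HIIT against SSMIT.
- Time main effect: change over the session, averaged over the two protocols.

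Only the last is not a comparison of the two protocols. The reading is reached by elimination.

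**2. What else changes along the time factor** (Phase 3, items 2, 4, 8 and 9)

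- Clock time: 30 min cycling + 30 min recovery = at least 60 min from first to last reading.
- Time without water: about 2 h at the pre-exercise reading; 2 h + 0.5 h + 0.5 h = about 3 h at the last.
- Readings on one eye: 1 + 6 = 7 per session, giving 7 × 6 / 2 = 21 pairs of time points.

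**3. How often a drift alone would be declared significant**

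From the protocol: n = 40, alpha = 0.05, 21 pairs. Assumed: two-sided tests, drift d (mmHg) between two readings, and SD s of 1.5 or 2.0 mmHg for a person's mean change over the two sessions. The true exercise effect is zero.

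The statistic is a noncentral t on 39 df with noncentrality d√40 / s. The critical value is 2.023 at 0.05 and 3.250 at 0.05/21 = 0.00238. For example, d = 0.5 and s = 2.0 give 0.5 × 6.325 / 2.0 = 1.58; d = 1.0 and s = 1.5 give 1.0 × 6.325 / 1.5 = 4.22.

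| Assumed drift | s | Unadjusted | Bonferroni, 21 pairs |
|---|---|---|---|
| 0 | either | 5% | 0.2% |
| 0.25 | 2.0 | 12% | 1% |
| 0.25 | 1.5 | 18% | 2% |
| 0.5 | 2.0 | 34% | 6% |
| 1.0 | 1.5 | 98% | 82% |

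**4. The same question for the planned ANOVA**

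A simulation of the 2 × 7 within-person ANOVA (Greenhouse-Geisser corrected, n = 40, 2,000 runs per scenario) used a linear drift common to both sessions and no exercise effect. Assumed SDs were 1.5 or 2.0 mmHg per reading, 2.5 between people and 1.0 between sessions. Averaging the change over two sessions gives s = √2 × SD / √2, so the per-reading SD equals s in step 3.

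- Time effect rejected: about 4% at zero drift; 17% (SD 2.0) and 32% (SD 1.5) at 0.5 mmHg; 72% and 95% at 1.0 mmHg.
- Interaction rejected: 3.4% to 4.5% throughout.

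The interaction holds its level because the drift was set equal in both sessions.

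**5. Whether the protocol secures equal drift**

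Item 1 allows a 3-hour window. If all readings of a session of at least 60 min fall inside it, a participant's two start times can still differ by up to 180 − 60 = 120 min. Nothing requires them to match.

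**The case against.** The plan never says time effect, and in a two-way ANOVA the effect of exercise could mean the exercise-type factor. That stands as a caveat: a reader might infer that the plan expressly names the time effect as its test of exercise, and it does not. The time reading is still the more natural one, because a separate paired t test already compares the interventions.

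The rejection rates are simply power against an assumed drift. This also stands. At zero drift the test keeps its 5% level, and at 0.25 mmHg the Bonferroni comparison rejects in only 1% to 2% of trials. A reader might infer that a false exercise finding is likely; the documents give no drift or SD and cannot support that.

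The six recovery readings carry information. A change at 0 minutes that reverses by 30 minutes is not what steady drift, lengthening fluid restriction or accumulating readings would produce. That is partial evidence for exercise, so the within-session data are not uninformative. But the plan sets no such criterion, and the pattern would support a causal reading without settling it.

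Temperature, morning window, posture, eye and tonometer are standardised, and the water restriction already applies at the pre-exercise reading. The protocol gives no reason for that restriction; diurnal variation is the only one of these influences it names. These controls make sessions more alike but do not remove change within a session.

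Finally, a reader might infer that the HIIT-SSMIT contrast is either undermined or fully protected. Neither follows. Drift common to both sessions cancels in it, but the 8 to 11am window does not guarantee that drift is common.

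**Conclusion.** The concern holds as a limit on inference. The within-session change is an uncontrolled before-after comparison and cannot by itself be attributed to exercise. That follows from the design and does not depend on any assumed number. The size is unknown: the rates run from nominal at zero drift to near certainty at 1.0 mmHg with the smaller SD, and they rest on the assumed drift, SD and two-sided testing.

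The HIIT versus SSMIT comparison is the better-supported basis for a causal conclusion, on two conditions. Drift must be similar in a participant's two sessions, and participants must actually have done both protocols. The second is unclear: Schedule for phase 3 lists an undefined CME for Group A in Week 2 and SSMIT for Group B in both weeks, against item 3. Nothing in the text indicates that CME is a resting condition. The documents do not support the inference that the trial is invalid.

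**What to change.** 1. **Statistical Analysis.** Base the causal conclusion on HIIT versus SSMIT, through the protocol-by-time interaction. Replace the stated aim of evaluating the effect of exercise with comparing the IOP course after the two protocols. Report within-session change with confidence intervals, labelled as uncontrolled pre-post change, and note that a change which reverses during recovery is supportive but not conclusive.
2. **Phase 3, item 1.** Book each participant's two sessions at the same clock slot within the existing window and record the start time.
3. **Schedule for phase 3.** Reconcile the Week 2 entries with item 3, because the HIIT-SSMIT contrast depends on them.

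The cover letter suggests that the sessions are already complete. If so, apply the first change, say that it was made afterwards, and report any start times that were recorded.

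The cost is wording and booking: a narrower headline claim and less flexibility in scheduling. No resting session and no extra participants are needed for this narrower claim.

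### The unrestricted Bonferroni pairwise test on IOP, read as all 21 pairs of the seven readings, is valid but loses power for the six pre-versus-post contrasts that address the stated aim.

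*Combined protocol and SAP*

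**What the plan says.** Item 8 of the Exercise Protocol Phase sets the readings. One is taken before exercise ("Before each session, the participants IOP of the right eye will be measured using an iCare rebound tonometer TA01i"), and then "repeated IOP measurements will be taken immediately after (0min), 5, 10, 15, 20 & 30 minutes after the exercise session". That makes seven per session. Recruitment is set at 40, and item 3 of the same phase has every participant do both protocols.

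The Statistical Analysis section uses a two-way repeated-measures ANOVA "to evaluate the effect of exercise on IOP and interaction between groups and time", "followed by using Bonferroni post-hoc test for pairwise comparison". It names neither the factor whose levels are paired nor the set of pairs. The comparison between protocols has a test of its own: "A paired sample T test will be conducted to assess the difference of IOP levels between interventions". The significance rule is "A value of $p < 0.05$ is considered as significant", with no mention of one- or two-sided testing. The documents contain no sample-size calculation, expected change or SD.

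**The concern.** A Bonferroni correction divides the 5% error equally over every comparison in its family, so each extra comparison makes all the others harder to pass. There are only two protocols, and their difference has its own paired t test. Time is then the only factor with more than two levels, and an unrestricted pairwise test most naturally runs over all pairs of its seven levels. Most of those pairs compare one post-exercise time with another, and the plan poses no question about such differences.

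The stake is the description of when IOP changes after exercise and for how long. A real change from the pre-exercise reading at a given time could be reported as non-significant only because the threshold was lowered for comparisons that the plan does not ask about. That could make the effect look shorter than it is.

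**Working it through.** The plan states no power or sample-size figure, so there is none to reproduce.

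**Inputs from the documents:** seven readings per session (one pre, six post); n = 40, with each participant doing both protocols, so each contrast is within person on 39 df; alpha 0.05.

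**Assumptions:** two-sided tests; standardised within-person change (mean change divided by the SD of the change) from 0.3 to 0.8.

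**1. Number of pairs**
- All pairs: 7 × 6 / 2 = 21
- Pre-versus-post: 6
- Post-versus-post: 6 × 5 / 2 = 15, and 15/21 = 71%

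**2. Threshold per test**
- 21 pairs: 0.05/21 = 0.00238, critical |t| = 3.25
- 6 contrasts: 0.05/6 = 0.00833, critical |t| = 2.78

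**3. Power per contrast.** For a paired t test the statistic has a noncentral t distribution with 39 df and noncentrality d × √40. Power is the probability that |t| exceeds the critical value.

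| Assumed change d (SD) | 21 pairs | 6 contrasts | Gain (points) |
|---|---|---|---|
| 0.3 | 10.6% | 20.5% | 10 |
| 0.4 | 25.6% | 41.3% | 16 |
| 0.5 | 47.5% | 64.9% | 17 |
| 0.6 | 70.2% | 83.8% | 14 |
| 0.7 | 87.0% | 94.4% | 7 |
| 0.8 | 95.7% | 98.6% | 3 |

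The change detectable with 80% power falls from 0.652 to 0.576 SD. The ratio squared, (0.652/0.576)² = 1.28, is roughly the relative sample size. At d = 0.5, 80% power needs 65 participants with 21 pairs and 52 with six contrasts.

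**4. What Holm adds to the six contrasts.** By simulation with n = 40 and correlation 0.5 between contrasts:
- Equal effects of 0.5 SD at all six times: about 76%, against 65% for Bonferroni on six, a gain of about 11 points.
- Effect fading 0.5, 0.4, 0.3, 0.2, 0.1, 0: about 66% against 65% at the first time.
- Effect of 0.5 SD at one time only: about 65% for both.

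**5. The same comparison at other levels of testing**
- *Averaged over protocols.* If each protocol has a change of 0.5 SD and the two changes correlate 0.5 (assumed), the averaged contrast has d = 0.5 / √((1 + 0.5)/2) = 0.577. Power is 65% with 21 pairs and 80% with six contrasts.
- *Within protocol, one joint family.* There are 42 pairs (0.05/42 = 0.00119) or 12 contrasts (0.05/12 = 0.00417). At d = 0.5, power is 39% and 55%.

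Limiting the family raises power whenever the same contrasts are compared. Its size depends on the assumed effect.

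**The case against.** The strongest objection is that the 21-pair family is inferred. The sentence names no factor and also covers the interaction, so the sponsor could have meant the seven same-time comparisons between protocols, and then the count of 21 would not apply. This stands as a caveat. The separate paired t test for the protocol difference makes time pairs the likelier reading without settling it. The family is unnamed in either case and needs stating.

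The second objection is that a fix must be compared like for like. A time main effect averages the two protocols, which reduces noise. With the correlation of 0.5 assumed above, 21 averaged pairs have 65% power, no less than six contrasts tested within one protocol. Giving each protocol its own 5% family also lets the study-wide error approach 10%. Both points are correct. They bear on how the fix is worded. At the same level of testing the gain remains.

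Third, the larger Holm gain needs equal effects at all six times, which sits badly with an interest in how long an effect lasts. This stands, and 76% should not be the headline.

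Fourth, post-versus-post differences say something about recovery. That is fair, but the plan asks no such question, and those differences can be described without a test.

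A reader might infer that the planned analysis is invalid, or that the comparison of HIIT with SSMIT is compromised. The documents support neither. All-pairs Bonferroni controls the type I error, and the protocol comparison has its own paired t test, which this correction does not affect.

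**Conclusion.** The point holds as one of efficiency and specification. On the plain reading, 15 of 21 comparisons serve no stated question, and the six that do are tested at 0.0024 where 0.0083 would suffice. The counts are exact given that reading.

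The loss is about 3 to 17 points of power per contrast. It is largest near 0.5 SD and small for large changes. This rests on n = 40 with complete data, two-sided tests, and assumed changes of 0.3 to 0.8 SD. Holm never rejects fewer hypotheses than Bonferroni on the same family. Its extra gain at 0.5 SD runs from almost nothing to about 11 points, depending on how the effect is spread over time.

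**What to change.** Replace the all-pairs post-hoc test with planned contrasts: each post-exercise reading (0, 5, 10, 15, 20, 30 min) minus the pre-exercise reading of the same session, Holm-adjusted at 5%. Report post-versus-post differences descriptively.

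State the level at which the contrasts are tested:
- if the time main effect is tested, six contrasts averaged over protocols, in one Holm family;
- if they are tested within protocol, either one Holm family of 12, or an explicit statement that the 5% error is controlled separately within each protocol.

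This takes a sentence or two in the Statistical Analysis section and needs no new data or participants. In SPSS, the software the plan names, simple contrasts with the first time as reference give the six tests, and the Holm step is a short calculation on their p values. The cost is that no formal test remains between two post-exercise times.

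The cover letter describes the study in the past tense. If data have already been analysed, label the change as post hoc.

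### Cheap improvement, not an error: the crossover paired t-test uses neither period nor the IOP measured before each session, and so may lose precision

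*Combined protocol and SAP*

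**What the plan says.** All references are to the combined protocol and SAP.

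- **Design.** Phase 3 item 3: "Each participant will perform both sessions (SSMIT & HIIT) based on the group they were assigned to", with a four-day washout. This is a two-period crossover.
- **Size.** Phase 1 item 2: "40 participants will be chosen based on the inclusion and exclusion criteria through a randomized method". The split between Group A and Group B is not given.
- **Readings.** Phase 3 item 8: "Before each session, the participants IOP of the right eye will be measured". Six readings follow, at 0, 5, 10, 15, 20 and 30 minutes after exercise.
- **Clock time.** Phase 2: "For intraocular pressure assessment, all subjects will be measured at 10am", give or take an hour, with diurnal variation named as the reason. Phase 3 item 1: "The exercise sessions will be conducted in controlled room temperature (20-23C) between 8.00am to 11.00am". No line says that a participant's two sessions start at the same hour.
- **Schedule for phase 3.** "Week 1: Group A (HIIT) & Group B (SSMIT) : 10 participants/day". The Week 2 line gives Group A the label CME, which is not defined, and gives Group B SSMIT a second time.
- **Statistical Analysis.** A two-way repeated-measures ANOVA is planned "to evaluate the effect of exercise on IOP and interaction between groups and time", with Bonferroni post-hoc comparisons. Then: "A paired sample T test will be conducted to assess the difference of IOP levels between interventions".

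**The concern.** The sentence on the t-test leaves out two things that a crossover analysis can use.

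The first is period. If IOP shifts between the first and second week for reasons unrelated to the protocol, the shift enters the HIIT-minus-SSMIT difference with opposite signs in the two orders. At balanced order it cancels from the mean but stays in the variance.

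The second is the pre-session reading. If a participant's two sessions differ in something that moves the pre- and post-exercise readings together, the paired difference carries that noise. The text offers a candidate: sessions may fall anywhere in a three-hour window, and the protocol itself treats time of day as a source of IOP variation.

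Both would widen the interval for the protocol comparison, and both can be reduced with data already collected. The control of room temperature and fluids in Phase 3 may keep a week-to-week shift small.

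Two gaps in the text stand in the way. The Week 2 line conflicts with item 3, so period cannot yet be coded. The word *groups* in the ANOVA is not defined: it could mean protocol or, as with Groups A and B in the schedule, order.

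**Working it through.** **Inputs.** n = 40 (Phase 1 item 2). Two-sided 0.05 (Statistical Analysis gives 0.05; two-sided is assumed). Assumed, because the documents give no value: a 20/20 order; r, the correlation between the HIIT-minus-SSMIT differences in pre-session IOP and in post-exercise IOP at the time tested; and p, the week-to-week shift in units of the SD of the paired difference. That SD is set to 1. The plan states no effect size, SD or power, so it has no figure to reproduce.

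**Step 1: pre-session adjustment, no period shift.** With an intercept, order and one random uncentred covariate, the variance relative to the paired t-test is (1 − r²) × (1 + 1/36). Interval width relative to the paired t-test is the square root of that, times 2.026/2.023 (t on 37 and 39 df).

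| r | variance ratio | 95% interval width ratio |
|---|---|---|
| 0 | 1.028 | 1.016 |
| 0.2 | 0.987 | 0.995 |
| 0.3 | 0.935 | 0.969 |
| 0.5 | 0.771 | 0.879 |
| 0.7 | 0.524 | 0.725 |

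The variance ratio equals 1 at r = √(1 − 36/37) = 0.164; the width ratio equals 1 at r = 0.174. With equal variances, about 17% of the variance of the paired differences must therefore be shared by a session's pre and post readings before adjustment pays.

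In power terms, the paired t-test has 80% power at a difference of 0.454 SD. The adjusted analysis has 79% at r = 0 and 89% at r = 0.5.

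**Step 2: period omitted.** At 20/20 the SE of the paired t-test is inflated by √(1 + p² × 40/39):

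- p = 0.1: 1.005
- p = 0.25: 1.032
- p = 0.5: 1.121, with type I error falling to about 3%

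If order ends unbalanced, the bias is p × (n1 − n2)/n. At p = 0.5 this is 0.5 × 4/40 = 0.05 SD for 22/18, and 0.5 × 4/36 = 0.056 SD for 20/16 completers. Simulated type I error of the paired test in these cases (r = 0.5) is 3.7% and 3.8%, still below 5%.

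**Step 3: does the regression hold its level?** In simulation (20,000 runs per case; r = 0, 0.3, 0.5, 0.7; p = 0 and 0.5) its type I error was 4.8% to 5.3%.

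**Step 4: centring the covariate.** Subtracting the sample mean of the pre-session difference turns the intercept back into the unadjusted mean but keeps the smaller residual SE. Type I error is then 2 × P(t37 > 2.026 × √(1 − r²)) = 6.1%, 8.8% and 15.6% at r = 0.3, 0.5 and 0.7.

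**The case against.** **The planned test is defensible.** It is valid at balanced order, and an omitted period shift makes it conservative. This stands, and it is why the point is an improvement only. A reader might infer that a crossover analysis without a period term is wrong or biased. Step 2 does not support that: at balance there is no bias, and at the mild imbalances examined the bias is about 0.05 SD and type I error stays below 5%.

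**No benefit is shown from the documents.** This also stands. Neither r nor p is given, and nothing in the text fixes which side of r = 0.17 the trial falls on. The three-hour session window is a reason to expect some shared session noise, not a measure of it.

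**The ANOVA may already use the pre-session reading.** If that reading is a level of time and *groups* means protocol, the interaction compares the protocols on change from pre-session. The text does not say so, and the gap is certain only for the t-test. A reader might infer that *groups* must mean protocol, or must mean order. The visible text settles neither, and a Phase 3 figure is not shown.

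**Adjustment can be done badly.** Step 4 shows the hazard. It is avoided by one line in the plan.

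**A single summary test is tempting.** A reader might infer that the mean of the six post-exercise readings should become the one deciding test, above the ANOVA interaction. Neither adjustment requires that, and it changes the endpoint and the test hierarchy. Assume a difference of 0.454 SD at 0 and 5 minutes only, equal variances and a serial correlation of 0.7 per 5 minutes. The averaged effect is then 0.454 × 2/6 = 0.151 against an SD of about 0.73, giving power of about 25% at r = 0. An unadjusted paired test at one affected time has 54% at 0.05/6. If the effect lasts over all six times, averaging has about 97%. The documents do not say which pattern to expect, so this is not part of the recommendation.

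**Conclusion.** The point holds as a cheap, hedged improvement. The paired t-test, as described, uses neither period nor the pre-session IOP, and adjusting for both is likely to cost little and may help.

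With no period shift, the range runs from an interval about 1.5% wider (r = 0) to about 27% narrower (r = 0.7). A period shift of 0.5 SD, if present, would inflate the unadjusted SE by 12%; one of 0.1 SD, by 0.5%. These figures rest on n = 40 from the protocol and on an assumed 20/20 order, r and p.

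Two matters are firm from the text whatever r is: the Week 2 line and Phase 3 item 3 disagree, and the plan leaves both *groups* and the time point of the t-test undefined.

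**What to change.** 1. Reconcile the Week 2 schedule line with Phase 3 item 3, and record each participant's actual order. Period cannot be coded before this is done. This review takes no view on which passage is right.
2. Name the post-exercise time point or points for the between-protocol comparison. At each one, replace the paired t-test by a regression with one row per participant. The outcome is the HIIT-minus-SSMIT difference in IOP at that time. The terms are an intercept, order coded +1/−1, and the HIIT-minus-SSMIT difference in pre-session IOP. The intercept is the protocol effect at equal pre-session IOP.
3. Enter the pre-session difference uncentred, and say so in the plan.
4. If several times are tested, apply Bonferroni: 0.05/6 = 0.0083 for all six.
5. Keep the ANOVA in its planned role. State what *groups* means in it and whether the pre-session reading is a level of time.
6. Report the unadjusted paired t-test as a sensitivity analysis.

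**Cost.** A few lines of SAP text and an ordinary regression that SPSS 23 can fit; no new data. It uses two degrees of freedom (37 instead of 39). With no period shift, precision is slightly worse below r of about 0.17. The cover letter describes the study in the past tense. If the data have already been analysed, the regression can still be run but should be labelled as not prespecified.
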